8.2.4 Electrocardiograms

Resting 12-lead ECGs will be recorded at screening, baseline and as clinically indicated throughout the study. ECGs should be obtained after the patient has been in a supine position for 5 minutes and recorded while the patient remains in that position. ECG during screening and at the Week 2 visit within 1 hr prior to the start of the first study treatment. Thereafter as clinically indicated. Baseline and abnormal ECG at any time in triplicate, others single..

In case of clinically significant ECG abnormalities, including a QTcF value >470 ms, 2 additional 12-lead ECGs should be obtained over a brief period (e.g., 30 minutes) to confirm the finding.

Situations in which ECG results should be reported as AEs are described in Section 10.3.1.

8.2.5 Vital signs

Vital signs (blood pressure [BP], pulse, temperature, and respiration rate) will be evaluated according to the assessment schedules. Body weight is also recorded at each visit along with vital signs.

First infusion

On the first infusion day, patients will be monitored and vital signs collected/recorded in eCRF prior to, during and after infusion of IP as presented in the bulleted list below.

BP and pulse will be collected from patients in the I-O arms before, during, and after each infusion at the following times (based on a 60-minute infusion):

- Prior to the beginning of the infusion (measured once from approximately 30 minutes before up to 0 minutes [i.e., the beginning of the infusion])
- Approximately 30 minutes during the infusion (**halfway** through infusion)

- At the end of the infusion (approximately 60 minutes \pm 5 minutes). If the infusion takes longer than 60 minutes, then BP and pulse measurements should follow the principles as described above or be taken more frequently if clinically indicated. A 1-hour observation period is recommended after the first infusion of durvalumab and tremelimumab.

Subsequent infusions

BP, pulse and other vital signs should be measured, collected/recorded in eCRF prior to the start of the infusion. Patients should be carefully monitored and BP and other vital signs should be measured during and post infusion as per institution standard and as clinically indicated. Any clinically significant changes in vital signs should be entered onto an unscheduled vital signs CRF page.

8.2.6 Clinical laboratory tests

Blood and urine samples for determination of clinical chemistry, hematology, and urinalysis will be taken at the times indicated in the assessment schedules and as clinically indicated (see **Table 2** through **Table 5**).

Clinical laboratory safety tests, including serum pregnancy tests, will be performed in a licensed clinical laboratory according to local standard procedures. Sample tubes and sample sizes may vary depending on the laboratory method used and routine practice at the site. Urine pregnancy tests may be performed at the site using a licensed test (urine or serum pregnancy test). Abnormal clinically significant laboratory results should be repeated as soon as possible (preferably within 24 to 48 hours).

Additional safety samples may be collected if clinically indicated at the discretion of the Investigator. The date, time of collection, and results (values, units, and reference ranges) will be recorded on the appropriate eCRF.

The laboratory variables to be measured are presented in **Table 4** (clinical chemistry), **Table 5** (hematology), and

Table 6 (urinalysis).

Other safety tests to be performed at screening include assessment for hepatitis B surface antigen, hepatitis C antibodies and HIV antibodies.

The following laboratory variables will be measured:

Table 4. Clinical chemistry and other miscellaneous labs

Albumin	^a	Tests for ALT, AST, alkaline phosphatase, and total bilirubin must be conducted and assessed concurrently. If total bilirubin is $\geq 2 \times$ upper limit of normal (and no evidence of Gilbert's syndrome) then fractionate into direct and indirect bilirubin.
Alkaline phosphatase ^a		
ALT ^a	^a	
Amylase ^b	^b	
AST ^a	^b	
Bicarbonate ^c	^b	
Bilirubin, total ^a	^b	
Calcium	^c	
Chloride ^c	^c	
Creatinine	^c	
Creatinine clearance ^c	^c	
Gamma glutamyltransferase ^c	^d	
Glucose	^d	
Lactate dehydrogenase	^d	
Lipase ^b	^d	
Magnesium ^c		
TSH		
T3, free ^d		
T4, free ^d		

Abbreviations: ALT Alanine aminotransferase; AST Aspartate aminotransferase, TSH Thyroid Stimulating Hormone

Table 5. Hematology

Absolute neutrophil count	
Hemoglobin	
Absolute lymphocyte count	
Platelet count	

Note: For coagulation parameters, activated partial thromboplastin time and international normalized ratio are to be assessed at baseline and as clinically indicated

Table 6. Urinalysis

Urinalysis should be done at baseline (screening) and then as clinically indicated

Bilirubin	
Blood	
Color and appearance	
Glucose	
Ketones	
pH	
Protein	
Specific gravity	

Note: Microscopy should be used as appropriate to investigate white blood cells and use the high power field for red blood cells.

If a patient shows an AST or ALT $\geq 3 \times$ ULN together with total bilirubin $\geq 2 \times$ ULN, refer to **Appendix 1** for further instructions on cases of increases in liver biochemistry and evaluation of Hy's Law. These cases should be reported as SAEs if, after evaluation, they meet the criteria for a Hy's law case or if any of the individual liver test parameters fulfill any of the SAE criteria.

All patients should have further chemistry profiles performed at 30 days (± 3 days), 2 months (± 1 week) and 3 months (± 1 week) after permanent discontinuation of IP (see Study Schedule in Section 8).

Any clinically significant abnormal laboratory values should be repeated as clinically indicated and recorded on the eCRF. Situations in which laboratory safety results should be reported as AEs are described in Section 10.3.6.

All patients with Grade 3 or 4 laboratory values at the time of completion or discontinuation from IP must have further tests performed until the laboratory values have returned to Grade 1 or 2, unless these values are not likely to improve because of the underlying disease.

8.3 Biological sampling procedures

8.3.1 Biomarker sampling and evaluation methods

Peripheral blood samples will be collected as per the study schedule. Samples will be processed for CTCs, and plasma for ctDNA analysis. All the samples will be stored in the Translational Research Enhancement Core of the Hopkins Conte GI Center.

8.3.6 Protocol Completion

Following completion of this study, samples will remain in storage as described above. Access to these samples will only be granted following IRB approval of an additional protocol, granting the rights to use the material. The PI will report destroyed samples to the IRB if samples become

unsalvageable because of environmental factors or if a patient withdraws consent. Samples will also be reported as lost if they are lost in transit between facilities or misplaced by a researcher.

8.3.7 Withdrawal of informed consent for donated biological samples

If a patient withdraws consent to the use of donated samples, the samples will be disposed of/destroyed, and the action documented.

All biological samples from that patient stored in our Core Center will be immediately identified, disposed of/destroyed, and the action documented. Furthermore, clinical or research data collected from the patient will also be destroyed from the database. We will notify both the patient and AstraZeneca.

9. DISEASE EVALUATION AND METHODS

9.1 Measure of Objective Response

Tumor response to treatment will be assessed by modified response evaluation criteria in solid tumors (mRECIST) which takes into account reduction in viable tumor using contrast-enhanced radiologic imaging rather than strict tumor size (Lencioni R, 2011). Conventional RECIST criteria can be misleading when applied to locoregional therapies in HCC and mRECIST adapted the concept of viable tumor-tumoral tissue showing uptake in arterial phase of contrast-enhanced radiologic imaging techniques. mRECIST has been adapted by the AASLD-JNCI (Journal of the National Cancer Institute) guidelines. The measurement of the longest diameter of the viable tumor may be challenging in lesions showing partial internal necrosis. Therefore, the measurement of the viable tumor should be performed on CT or MRI obtained in the arterial phase, when the contrast between viable vascularized tumor tissue and non-enhancing necrotic tissue is the highest. The longest diameter of the viable tumor is not necessarily located in the same scan plane in which the baseline diameter was measured. The measurement of the viable tumor diameter should not include any major intervening areas of necrosis.

Assessment of Target Lesion Response: mRECIST Assessment for HCC Following the AASLD-JNCI Guideline
CR = Disappearance of any intratumoral arterial enhancement in all target lesions
PR = At least a 30% decrease in the sum of diameters of viable (enhancement in the arterial phase) target lesions, taking as reference the baseline sum of the diameters of target lesions
SD = Any cases that do not qualify for either partial response or progressive disease
PD = An increase of at least 20% in the sum of the diameters of viable (enhancing) target lesions, taking as reference the smallest sum of the diameters of viable (enhancing) target lesions recorded since treatment started

AASLD, American Association for the Study of Liver Diseases; JNCI, Journal of the National Cancer Institute; HCC, hepatocellular carcinoma; mRECIST, modified Response Evaluation Criteria in Solid Tumors; CR, complete response; PR, partial response; SD, stable disease; PD, progressive disease.

As response to immunotherapy may be delayed compared to conventional chemotherapy, patients with PD will have confirmatory assessment after 4 weeks from the initial assessment of PD in the absence of clinically significant deterioration. Treatment with durvalumab + tremelimumab would continue between the initial assessment of progression and confirmation for progression. In addition, patients may continue to receive durvalumab + tremelimumab beyond confirmed PD in the absence of clinically significant deterioration and if investigators consider that patients continue to receive benefit from treatment until the next surveillance imaging.

Patients who have disease control following completion of 12 months of treatment or patients who are withdrawn from durvalumab + tremelimumab treatment for reasons other than confirmed PD will continue to have objective tumor assessments (see Study Schedule in Section 8Error! Reference source not found.).

Confirmation of progression guidelines are set for the following reasons:

- for patient management and treatment decisions
- in the absence of significant clinical deterioration, to promote the collection of additional scans after the first radiologic mRECIST assessment of progressive disease (PD) in order to distinguish pseudoprogression from true radiologic progression, also known as mRECIST modified for confirmation of progression
- When scans are evaluated by Investigator and by BICR, to reduce informative censoring by Investigator assessments (Investigator assesses PD at a time-point earlier than does BICR).

Confirmed objective disease progression refers to either of the following scenarios: 1. clinical progression/deterioration followed by a radiologic verification scan (PD by mRECIST); or 2. in the absence of significant clinical deterioration, radiologic PD by mRECIST followed by a second radiologic confirmation scan with PD assessed according to the specific confirmation of progression criteria listed below. mRECIST modified for confirmation of progression refers to the second scenario above. The confirmatory scan should occur preferably at the next scheduled imaging visit and no earlier than 4 weeks following the date of the immediate prior assessment of mRECIST PD.

Immediate prior radiologic progression would be considered confirmed if any the following criteria are met in the confirmatory scan:

- $\geq 20\%$ increase in the sum diameters of target lesions (TLs) compared with the nadir at 2 consecutive visits, with an absolute increase of at least 5 mm in sum of diameters compared to nadir,
- and/or significant progression (worsening) of non-target lesions (NTLs) and/or of pre-existing new lesions at the confirmatory scan time-point compared with the immediate prior time-point (Note: Pre-existing new lesions are evaluated as NTLs at the confirmatory scan time-point),
- And/or additional new unequivocal lesions at the confirmatory scan time-point.

NOTE: In order to have confirmed objective disease progression, there should be two consecutive PD's, the first PD by mRECIST and the second PD using the confirmation of progression criteria

(above). If the first PD by mRECIST is not confirmed, continue with assessments until the next PD by RECIST 1.1, which in turn will need its own immediate subsequent confirmation scan.

In the absence of significant clinical deterioration, treatment with study drug may continue between the initial assessment of progression and the scan to confirm progression.

If the confirmation scan confirms progression, then the date of the prior scan with PD should be declared as the date of progression.

If progression is not confirmed, in the absence of significant clinical deterioration, then the patient should continue study drug and on-treatment assessments until the next PD which will also require a follow-up confirmation scan. **If the first PD is not confirmed by the immediate next scan, then the Investigator should not change the PD assessment of the first scan.**

If a patient discontinues treatment (and/or receives a subsequent anticancer therapy) prior to radiologic progression, then the patient should still continue to be followed until confirmed objective disease progression.

Following confirmed progression, patients should continue to be followed up for survival every 2 months (8 weeks) as outlined in the follow-up schedules of assessments.

Patients in the durvalumab + tremelimumab combination arm who complete 4 doses/dosing cycles (with clinical benefit per Investigator judgment) and subsequently have PD during treatment with durvalumab alone may restart combination treatment if they meet eligibility criteria for retreatment (see **Section 5.2.2**). Patients who restart treatment after PD must have a baseline tumor assessment within 28 days of restarting treatment with durvalumab + tremelimumab combination therapy; all further scans should occur every 8 weeks (± 7 days) relative to the date of previous scheduled study scan until confirmed disease progression

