11.2.2 Efficacy analyses

The primary endpoint is objective response. Objective response rate, defined as the percent of patients with at least one visit response of CR or PR via mRECIST and will be based on the Evaluable Population.

As a secondary endpoint, the response of non-target lesions will be described. Other secondary efficacy endpoints include duration of response, 6-month progression-free survival, and overall survival (OS). Duration of response is defined as date of having CR or PR to the date of progression per mRECIST among the patients who have CR or PR. Progression free survival will be defined as the time from the date of start of the treatment until the documentation of disease progression according to mRECIST or death due to any cause, whichever occurs first. Patients who have not progressed or died at the time of the analysis will be censored at the time of the latest date of assessment from their last evaluable mRECIST assessment. Kaplan-Meier

curves will be used to characterize PFS and OS, and 6-month PFS will be estimated from Kaplan-Meier.

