11.3 Determination of sample size

The standard of care treatment with DEB-TACE results in a objective response rate (ORR) of 30%. The regimen would be considered of insufficient activity for further study if the ORR is 30% or less, and the minimum required level of efficacy that would warrant further study with the proposed regimen is a 60% response rate. An optimal Simon two-stage design is planned. A total of 8 patients will be entered in the first stage. If ≤ 2 subjects respond, the treatment will be terminated and we will conclude the regimen is ineffective. If ≥ 3 subjects respond, then additional 12 patients will be studied. If a total of 8 or fewer subjects respond in stage one and two combined, the regimen is considered ineffective. If a total of 9 or more respond, we conclude the regimen is promising and warrants further study. The maximum sample size will be 20 evaluable patients. To account for 10% unevaluable patients who do not receive durvalumab/tremelimumab following DEB-TACE, or do not have any on treatment scans for reasons other than death, we plan to enroll 22 patients.

This design provides 90% power to detect a 30% absolute increase in ORR, from 30% to 60%, with one-sided type I error 0.1. The chance of stopping early for lack of efficacy at the interim analysis is 0.55, if the response rate is 30%.

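### The primary response count has no cut-off at progression, although Section 9.1 allows study drug past confirmed PD and a restart of the combination after PD

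*Combined protocol and SAP*

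**What the plan says.** - **Primary endpoint (11.2.2).** ORR is "the percent of patients with at least one visit response of CR or PR via mRECIST". Nothing ends the count at progression, at a restart or at new therapy. The synopsis calls the analysis one of best overall response but gives no assessment window. The evaluable set in 11.1.2 restricts which patients count, not which visits.
- **Reference for PR (9.1, response table).** A fall of at least 30% is judged "taking as reference the baseline sum of the diameters of target lesions".
- **Treatment past confirmed PD (9.1).** "patients may continue to receive durvalumab + tremelimumab beyond confirmed PD in the absence of clinically significant deterioration". The same sentence adds two limits: the investigator must see continuing benefit, and the provision runs until the next surveillance scan.
- **Restart after PD (9.1, last paragraph).** Patients who complete four combination doses and then progress on durvalumab alone may restart the combination if they meet the Section 5.2.2 retreatment criteria. "Patients who restart treatment after PD must have a baseline tumor assessment within 28 days of restarting treatment with durvalumab + tremelimumab combination therapy", and scans then continue every 8 weeks until confirmed progression.
- **Progression date (9.1).** A confirmed progression is dated back to the earlier of the two PD scans.
- **PFS and duration of response (11.2.2).** PFS ends at documented mRECIST progression or death. Duration of response runs from CR or PR to progression.

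**The concern.** Taken together, these provisions let a patient be scored three ways that do not agree. Suppose a patient has no CR or PR, has confirmed PD, stays on study drug, and then shows a CR or PR at the next scan. That patient is a PFS event dated to the first PD scan. Under 11.2.2 the same patient is also a success on the primary endpoint. The duration of response would begin after the progression date that is meant to end it, so it has no valid value.

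A restart adds a second scan that the protocol calls a baseline, and no text says which one governs PR.

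The trial's conclusion is a raw count of responders, with hurdles of 3 of 8 and 9 of 20. A response that first appears after the regimen has failed by the protocol's own progression rule is weak evidence that the regimen beats the 30% DEB-TACE rate, yet it would count in full.

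**Working it through.** **1. The plan's own figures (11.3).** Inputs: p0 = 0.30, p1 = 0.60; first stage n1 = 8 ("A total of 8 patients will be entered in the first stage"); stop at 2 or fewer ("If ≤ 2 subjects respond, the treatment will be terminated and we will conclude the regimen is ineffective"); 12 more patients otherwise; success at 9 or more of 20.

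P(success | p) = Σ over x = 3…8 of Bin(8, x; p) × P(Bin(12, p) ≥ 9 − x).

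At p = 0.30 the terms are:

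| x | Bin(8, x) | P(≥ 9 − x of 12) | product |
|---|---|---|---|
| 3 | 0.2541 | 0.1178 | 0.0299 |
| 4 | 0.1361 | 0.2763 | 0.0376 |
| 5 | 0.0467 | 0.5075 | 0.0237 |
| 6 | 0.0100 | 0.7472 | 0.0075 |
| 7 | 0.0012 | 0.9150 | 0.0011 |
| 8 | 0.0001 | 0.9862 | 0.0001 |

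The sum is 0.0999 (stated 0.1). At p = 0.60 the power is 0.912 (stated 90%). The chance of stopping early at p = 0.30 is P(Bin(8, 0.30) ≤ 2) = 0.552 (stated 0.55). The stated design reproduces.

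**2. How close the decision is.** No assumed rate is needed here. Eight responders is a negative trial and nine a positive one. Under p0, the chance of passing stage one and finishing on exactly 8 is Σ over x = 3…8 of Bin(8, x; 0.30) × Bin(12, 8 − x; 0.30) = 0.085. In that situation one late response reverses the conclusion.

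**3. Which baseline (hypothetical diameters).** Original sum 50 mm, with no smaller sum before progression. PD at 65 mm: 65/50 − 1 = +30%. After a restart with 65 mm as the new baseline, the sum falls to 45 mm.
- Against the restart baseline: 45/65 − 1 = −31%, which is PR.
- Against the original baseline: 45/50 − 1 = −10%, which is not PR.

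**4. Sensitivity of type I error.** The documents give no rate for this path, so f and r are assumptions. Let f be the share of non-responders who take the path and r the share of those who then show CR or PR, each from 10% to 30%. Put q = f × r. With a true pre-progression response rate of 0.30, the counted rate is 0.30 + 0.70q.

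- *Both looks:* put p = 0.30 + 0.70q in the formula of step 1.
- *Final look only:* stage one is decided on X ~ Bin(8, 0.30) with X ≥ 3. The final count is X + Bin(8 − X, q) + Bin(12, 0.30 + 0.70q).

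| f, r | q | counted rate | extra responders in 20 (20 × 0.70q) | both looks | final look only |
|---|---|---|---|---|---|
| none | 0 | 0.300 | 0 | 0.100 | 0.100 |
| 10%, 10% | 0.01 | 0.307 | 0.14 | 0.113 | 0.110 |
| 20%, 20% | 0.04 | 0.328 | 0.56 | 0.157 | 0.144 |
| 30%, 30% | 0.09 | 0.363 | 1.26 | 0.249 | 0.203 |

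The final-look column suits the restart path better: such a response needs four doses, then progression, then further scans, and may arrive after the 8-patient decision. The timing of that decision is not stated.

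**The case against.** The case for a smaller point is a good one, and most of it stands.

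- **The restart text fits this trial poorly.** It refers to a combination arm and four doses. The synopsis and Section 3 describe a single arm with tremelimumab given once, and Figure 2 shows one tremelimumab dose. The wording is still current, and Sections 1.3.5.2 and 8.2.3 also describe four combination cycles. The response-window gap does not depend on it, because treatment past confirmed PD already leads to a further scan. Only the two-baseline problem needs the restart text.
- **The retreatment criteria cannot be seen.** The body of Section 5.2.2 is not in the text available. That is not a fault in the plan, but the criteria may leave few or no patients eligible.
- **Data after PD are limited.** Treatment past confirmed PD runs to the next scan. Follow-up after confirmed progression is for survival, and scans after stopping for PD are optional (Figure 2, note e).
- **The intended reading may be conventional.** Best overall response under mRECIST may be meant to stop at progression, and the pre-treatment scan is the natural reference. But 9.1 rewrites the progression rules at length without linking them to the response count, so the primary endpoint needs the rule in writing.

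A reader might infer three stronger things that the documents do not support:

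- *That the plan expressly pairs confirmed PD with a fresh baseline.* It does not. The restart paragraph says PD without requiring confirmation, and the provision for treatment past confirmed PD sets no new baseline.
- *That every response after progression inflates the count.* Patients with CR or PR before PD already count. Only those without an earlier response can add.
- *That PR after a restart is to be measured from the new scan.* The text leaves this open.

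**Conclusion.** The concern holds in a limited form. Under 11.2.2 as written, a first CR or PR after confirmed PD counts towards the Simon decision, although the patient is already a PFS event and has no calculable duration of response. After a restart, the reference baseline for PR is undefined.

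The firm measure of size is the one-patient margin between 8 and 9 of 20. The type I error ranges, about 0.11–0.20 at the final look only and 0.11–0.25 at both looks, rest wholly on assumed values of f and r. They also apply f to all non-responders, including early progressors who could never reach a restart, so they lean high. They should not be read as the trial's actual error rate: if the window closes at confirmed progression, the design keeps its 0.0999.

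This should be corrected before responses are scored. How many patients it would affect is unknown and may be few.

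**What to change.** In 11.2.2 and in the synopsis, state that:

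1. Objective response counts only CR or PR visits before confirmed progression, dated to the first of the two PD scans as 9.1 already provides, and before any restart of the combination.
2. The reference for PR is always the original pre-DEB-TACE baseline.
3. An unconfirmed PD does not close the window, so pseudoprogression followed by response is still counted.
4. Responses after confirmed PD or after a restart are listed separately and do not enter the 3-of-8 or 9-of-20 decision.

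Duration of response then always starts before it ends, and ORR and PFS no longer contradict each other for the same patient.

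Separately, the restart paragraph in 9.1 and the four-cycle wording in 1.3.5.2 and 8.2.3 must be reconciled with the single-dose tremelimumab regimen in the synopsis and Section 3. Which of these is right is for the sponsor and the investigator to settle.

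The cost of the statistical change is two or so sentences and one descriptive line in the report. It alters no treatment. The counted ORR may be slightly lower.
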